Thus, research to reduce these parents' exposure to stress and, moreover, improve parental responses to stress, may improve the wellbeing of both parents and their children. Yet, a treatment focused on the psychosocial needs in relation to stress and allostatic load of parents of children with ASD has not been developed. Research is warranted to examine and intervene upon parental stress. This study aims to design and develop a resiliency intervention to provide support to parents of children with ASD. This intervention will be a modified version of [name] evidence-based 8-week multimodal treatment which is designed to promote adaptation to stress and promotion of resiliency. The program is an 8 session, 1-1.5 hours a week multi modal intervention that incorporates relaxation techniques, stress awareness discussion, and adaptive strategies for coping with stress. This study will refine an 8-session group virtual-delivered resiliency treatment program consisting of 8 virtual group 1-1.5 hour sessions. The goal of this study would be to advance our ultimate objective to implement a national parental resiliency program.

II. SPECIFIC AIMS

The proposed research has the following objectives:

Specific Aim 1 (Phase II): Informed by Phase I findings, (approved in a previous IRB protocol #2016P001698), we aim to develop and determine the feasibility (by assessing the number of sessions attended and adherence to Relaxation Response practice) and acceptability (assessed using the Participant Feedback Survey) of an 8-session Relaxation Response Resiliency (SMART-3RP) program for parents of children with ASD.

Hypothesis: The SMART-3RP virtual delivery will be feasible to implement and acceptable to parents of children with ASD.

Primary Aim 2 (Phase III): To test the effectiveness of a pilot waitlist controlled trial on improving resiliency, as measured using the General Self-Efficacy Questionnaire, Current Experiences Scale, and the Visual Analogue 0-10 scales (including stress, distress, coping, and physical discomfort), and on improving stress reactivity (as measured by the Measure of Current Status-A), growth enhancement (as measured by the Cognitive and Affective Mindfulness Scale-Revised), and parental stress (as measured by the Parental Stress Scale).

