Groups consist of no more than 8 participants, and can be smaller as well. The group consists of participants, parents of children with ASD, as well as a group leader and a study staff member. The study staff member is fully trained in observing SMART-3RP groups, and will be setting up the videoconferencing group each week, and helping participants connect to the group.

At the start of the program, the leader clearly discusses the importance of confidentiality and asks that participants sit in a room alone, not record the sessions, and not share any other group members' personal information with others outside of the group. The program also discusses goal setting to help partcipants identify some personal goals and strategize ways to begin tackling them. These goals are addressed through weekly practice.

Homework and exercises

Homework each week involves practicing the skills discussed in the previous session. Participants are encouraged to listen to the audio recordings of meditation exercises that come with the program manual. In each session, participants are encouraged to discuss their thoughts about their practice, what they liked, and what they did not like. No one is required to do any practice that they do not find helpful. We collect copies of the practice logs. The practice logs include:

- a) Types of RR exercises practiced and duration of practice
- b) Appreciations: participants are asked to list three things they appreciated each day of the week—this exercise helps bring awareness to the positive aspects of our lives, and allows us to re-live enjoyable moments through remembering them
- c) SMART goals—participants are encouraged to write down specific small goals for the week such as, "take a walk outside at least twice"—to help them moved towards their larger goals

Other exercises that we practice in the SMART-3RP include exercises that help participants identify specific stressors, how they feel when they experience stress, what types of thoughts they have, and what it is about the particular incident that makes them feel stressed. We do a practice exercise as a group and encourage participants to practice for homework by thinking about their thoughts and feelings when they get stressed. They are also encouraged to complete a coping log if they are interested. They do not turn this into us as it is just for their own benefit.

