The process of developing the Benson-Henry Institute's SMART-3RP is further described in [name] article, The Development of a Patient-Centered Program Based on the Relaxation Response: The Relaxation Response Resiliency Program (3RP). The current program that will be used in this study is an adapted version of the original program, and is tailored to the needs of parents of children with ASD.

Differences in the adapted program include:

-Examples in each exercise tailored to parents

-An introduction at the beginning of the program about parental stress, and how we hope to provide useful stress management skills to help parents of children with ASD.

-A list of recommended resources for parents if they are interested (list serves etc)

Participants randomized to Immediate or Waitlist will participate in the SMART-3RP program. Participants in the Immediate arm will be encouraged to practice the skills taught in the program

during the 3 month follow up period after completion of the 8 session SMART-3RP. Participants in the Waitlist arm will wait for approximately 3 months before beginning the SMART-3RP.

Participants in both groups will be given questionnaires at the same timepoints (baseline, 3 month post enrollment, and 6 month post enrollment). Study staff will email these questionnaires to the participants via the REDCap system. Participants who have not responded within two weeks of each time point will be contacted by telephone to ensure receipt of study data.

Figure 1 (below) illustrates the administration of questionnaires in both groups.

Figure 1. Study Design.

Remuneration

Participants will be given a \$20 gift certificate for completing 3 mo. survey and another \$20 gift certificate for completing the 6 mo. survey assessment.

Participants may also be compensated up to \$40 for their hair samples (\$20 for the first and \$20 for the second). Compensation will be provided for those who have already submitted at least their baseline hair sample, and for all future participants interested in completing their hair samples.

VI. BIOSTATISTIC ANALYSIS

We plan to conduct a pilot trial of a virtual-based SMART-3RP intervention for parents of children with ASD. Participants in this trial will be randomized to one of two groups: 1) Immediate SMART-3RP intervention, or 2) Waitlist control SMART-3RP group (starting approximately 3 months after enrollment).

The following questions will be assessed:

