1) Is the virtual SMART-3RP feasible and acceptable for parents who have children with ASD?

Feasibility will be assessed using attendance and homework completion (i.e. 6/8 sessions and homework completion-See practice note).

Acceptability will be assessed using a Participant Feedback questionnaire (See Feedback questionnaire attached).

2) Is the virtual SMART-3RP program effective for parents of children with ASD?

a) Is there a significant difference in primary and secondary outcome measures between participants in the Immediate and Waitlist SMART-3RP groups at 3 mo. post enrollment?

We will use paired samples t-tests to compare within group differences on primary and secondary outcome measures from 3 mo. to baseline for the Immediate and Waitlist Groups. Primary outcome measures are the General Self-Efficacy Questionnaire (GSE), Current Experiences Scale (CES; from the Post Traumatic Growth Inventory), and the Visual Analogue 0-10 scales (VAS; measuring stress, distress, coping, and physical discomfort). Secondary outcome measures are: the Measure of Current Status-A (MOCS-A; to assess stress reactivity), Cognitive and Affective Mindfulness Scale-Revised (CAMS-R; to assess growth enhancement), and the Parental Stress Scale (PSS; to assess parental stress).

We will then use independent samples t-tests to compare the difference between the Immediate group's 3 months post enrollment and baseline assessment results with the difference between the waitlist group's 3 months and baseline assessment results on primary and secondary outcome measures.

b) Among participants randomized to both conditions, will there be improvements in primary and secondary outcome measures from pre-post SMART-3RP (IG: assessments from baseline-3 mo.; WG: from 3-6 mo.)?

We will use paired samples t-tests to compare all primary and secondary assessments from pre-post SMART-3RP (for the IG, assessments are from baseline-3 mo.; for the WG, assessments are 3 mo. to 6 mo.).

c) Among the Immediate group only, will the changes from baseline to 3 months post enrollment (end of treatment) be sustained at 6 months post enrollment (3 months post treatment)?

We will use paired samples t-test to assess within-group differences in long-term outcomes. We will compare measures at the 6 months assessment to measures at the 3 months assessment for the Immediate group.

3) Will the virtual delivery SMART-3RP be effective in reducing participants' stress levels, measured by hair cortisol?

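### SMART-3RP is delivered in interacting groups of at most 8, but the questionnaire t-tests treat participants as independent; a group-adjusted sensitivity analysis should sit beside the 2a and 2b tests

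*Protocol*

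**What the plan says.** Allocation is individual and 1:1 (Protocol IV, Randomization), with about 70 participants in total (Protocol III, Recruitment). Treatment is then given in groups (Protocol V, What does it involve?): "Groups consist of no more than 8 participants, and can be smaller as well". Each group has a leader and a staff member who "will be setting up the videoconferencing group each week". Members interact (Protocol V, Homework and exercises): "In each session, participants are encouraged to discuss their thoughts about their practice, what they liked, and what they did not like". They also do a practice exercise together.

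The control arm is not grouped when the main comparison is made (Protocol V, SMART-3RP Development): "Participants in the Waitlist arm will wait for approximately 3 months before beginning the SMART-3RP".

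For the questionnaires, Protocol VI gives:
- **2a:** paired t-tests within each arm from baseline to 3 months, then "We will then use independent samples t-tests to compare the difference between the Immediate" arm's change with the Waitlist arm's change.
- **2b:** "We will use paired samples t-tests to compare all primary and secondary assessments from pre-post SMART-3RP".
- **2c:** "We will use paired samples t-test to assess within-group differences in long-term outcomes", from 3 to 6 months in the Immediate arm.

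The Study Aims table in the SAP lists the same kinds of test. Neither document mentions treatment group, ICC, a design effect, or a limit of the conclusions to the groups run. The only mixed model is for hair cortisol (Protocol VI, question 3), and its random effects are not specified.

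**The concern.** A t-test takes each participant's change as an independent observation. People who share a leader, a weekly discussion and the same fellow members may change together. If they do, the mean change in a treated arm varies more from one set of groups to another than the t-test allows, and p-values are too small for statements about the programme as it would run in new groups.

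The tests are not affected equally:
- **2a between arms:** only the Immediate arm is grouped at 3 months, so the comparison is partially nested and the effect is diluted.
- **Immediate paired test in 2a, and 2b:** every observation is on a treated, grouped participant, so the effect is larger.
- **2c:** affected only if changes from 3 to 6 months still correlate within group after sessions end. A standard error that is too small would then make a false decline as easy to declare as a false further gain.
- **Waitlist baseline-to-3-month test, and the feasibility and acceptability aim:** unaffected.

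At stake is how far a significant result can be carried. The protocol looks beyond these groups, though only as a longer-term aim (Protocol I): "The goal of this study would be to advance our ultimate objective to implement a national parental resiliency program".

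**Working it through.** The plan gives no power calculation, ICC, alpha or number of groups, so there is no figure of its own to reproduce.

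**Inputs from the documents.** About 70 participants at 1:1 gives 35 per arm. The maximum group size is 8, so the Immediate arm needs at least 35/8 = 4.4, that is five groups.

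**Assumptions.** All 35 per arm analysed; two-sided 0.05; change-score SD 1 in both arms; average effect zero across groups; ICC of the change score 0.01, 0.05 or 0.10. Two layouts: five groups of 7, and eight groups of 4 plus one of 3.

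**Formulas.** With group sizes m, the design effect in treated participants is DE = 1 + (Σm²/35 − 1) × ICC. The variance of a paired mean change is multiplied by DE. The variance of the 2a difference is multiplied by (DE + 1)/2, because only one arm is grouped. The actual error of a nominal 5% test is about 2 × [1 − Φ(1.96/√ratio)], where the ratio is that multiplier.

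**Five groups of 7, ICC 0.05.** Σm²/35 = 245/35 = 7, so DE = 1 + 6 × 0.05 = 1.30.
- 2a: ratio 2.30/2 = 1.15; 1.96/√1.15 = 1.83; error 6.8%.
- Paired: ratio 1.30; 1.96/√1.30 = 1.72; error 8.6%.

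**Groups of about 4, ICC 0.05.** Σm²/35 = (8 × 16 + 9)/35 = 3.91, so DE = 1 + 2.91 × 0.05 = 1.15. The errors are 5.9% (2a) and 6.7% (paired).

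Simulation of the t-tests agrees to within about 0.2 points:

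| Layout | Test | ICC 0.01 | ICC 0.05 | ICC 0.10 |
|---|---|---|---|---|
| Five groups of 7 | 2a between arms | 5.3% | 6.7% | 8.5% |
| Five groups of 7 | Paired, one treated arm | 5.6% | 8.5% | 12% |
| Eight of 4, one of 3 | 2a between arms | 5.2% | 5.9% | 6.7% |
| Eight of 4, one of 3 | Paired, one treated arm | 5.3% | 6.6% | 8.4% |

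The protocol does not say whether 2b pools the arms. If it does, with the same group sizes, the paired figures change by no more than 0.2 points.

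**Does adjustment work?** With five groups of 7 and ICC 0 to 0.10, comparing group means with Waitlist individuals using Satterthwaite df gives a type I error of 5.2 to 5.3% for 2a. A one-sample t-test on group mean changes gives 5.0% for 2b.

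**What does it cost in power?** Five groups of 7, ICC 0.05: the variance of a group mean is 0.05 + 0.95/7 = 0.186.
- 2b, change of 0.5 SD: SE = √(0.186/5) = 0.193; 0.5/0.193 = 2.59 on 4 df; power about 51%, against 79% for the paired t-test.
- 2a, difference of 0.7 SD: SE = √(0.186/5 + 1/35) = 0.256; 0.7/0.256 = 2.73 on about 11.7 df; power about 70%, against 81% for the t-test.

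At ICC 0.10 the falls are from 77% to 43% (2b) and from 80% to 64% (2a).

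**The case against.** **The ICC is unknown and may be very small.** This stands. The programme is manualised, much of the practice is done alone with audio recordings, and some exercises need not be shared. Nothing in the documents favours 0.05 or 0.10 over 0.01, and groups may be smaller than 7. Loss to follow-up would also shrink groups and the design effect. Weekly discussion makes an ICC of exactly zero unlikely, but no more than that can be said.

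**Randomisation protects 2a.** This stands under a strict null in which the programme changes nobody's outcome. The 2a error rates above refer to a different null: group effects exist but average zero over groups that might have been run. The protection does not extend to the paired tests, which are not randomised comparisons.

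**Conclusions limited to the groups run are acceptable in a pilot.** They are, if labelled so. The plan has no such label, and it asks whether the programme is effective for parents of children with ASD in general.

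**Other weaknesses are larger.** The pre-post tests have no concurrent control, and a group-level standard error does not repair that. Six primary scales have no multiplicity rule; if they were independent, the familywise error would be 1 − 0.95⁶ = 26%. Both points are fair, but neither answers this one.

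**The adjusted tests are weak.** This stands. With about five groups, the adjusted 2b test in one arm has 4 df. That is why it should be a sensitivity analysis and should not decide by itself what may be claimed.

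**Conclusion.** The point holds as a minor, inexpensive improvement. The plan treats participants in groups and analyses their questionnaires as if they were independent. Under the stated assumptions, the false-positive rate for claims beyond the groups run lies between about 5.2% and 8.5% for the between-arm test, and between about 5.3% and 12% for paired tests in treated participants. At ICC 0.01 it is negligible.

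A reader might infer more than the documents support:
- **That the planned t-tests are invalid.** They remain usable as statements about the groups run, and 2a is protected under the strict null.
- **That 70 participants is the wrong number.** No power target is stated, so this cannot be judged.
- **That the bias always favours the programme.** In 2c it could equally produce a false decline.
- **That the adjusted result should overrule the t-test.** With so few groups, a non-significant adjusted result may reflect only low power.

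**What to change.** 1. Include treatment-group membership in the analysis dataset. Staff set up each group weekly, so it should be known; the documents do not say that it is recorded as a variable.
2. Keep the planned t-tests. Label those on treated participants, 2c included, as conditional on the groups run.
3. Name one group-adjusted sensitivity analysis for each of two questions:
   - **2a:** a group effect in the Immediate arm only. Either compare Immediate group means with Waitlist individuals using Satterthwaite df, or fit a partially nested mixed model with Satterthwaite or Kenward-Roger df.
   - **2b:** a one-sample t-test on group mean changes, or the mixed-model equivalent. The Immediate arm's paired test in 2a uses the same baseline-to-3-month change, so an arm-specific 2b analysis covers it.
4. Make these choices before outcome data are analysed. A choice before any data exist may no longer be possible, because the Remuneration text of the 2021 protocol refers to hair samples already submitted.
5. Report both results. If they disagree, say that evidence for the programme in new groups is uncertain.
6. In the hair cortisol mixed model, include a group effect for the Immediate arm, or label that result as conditional too.

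The cost is some SAP wording, one variable and the lower power shown above for the added analyses. Any ICC that is reported will be very imprecise: at a true value of 0.05 with five groups of 7, the median 95% interval is about −0.10 to 0.56.

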Primary Hypothesis: Patients randomized to the Immediate group will report significantly greater scores on the primary outcomes (measures of resilience) and on the secondary outcomes (measures of stress reactivity, growth enhancement, and parental stress) at 3 mo. post enrollment.

Secondary Aims: Among participants randomized to both conditions, to investigate the extent of pre-post changes in primary and secondary outcomes (Immediate: assessments from baseline-3 mo.; Waitlist: from 3-6 mo.).

Secondary Hypothesis: Scores on primary and secondary outcome measures will improve from pre-post intervention.

Secondary Aim 2: Among immediate condition group only, to assess whether end-of-treatment (3 mo. post enrollment) improvements will be sustained at 6-mo. post enrollment.

Hypothesis: These end-of-treatment effects will show sustained improvement on primary and secondary outcome measures from 3 to 6-mo. Post enrollment.

Secondary Aim 3: To pilot test the end-of-treatment effects of the SMART-3RP on parents' stress levels using hair cortisol. A mixed effects models approach will be used to examine group

differences in hair cortisol concentrations (HCC) at baseline and 3 mo. post enrollment. Pearson correlation or Spearman's rank correlation will be used to examine the association of HCC with each of our psychological outcomes.

Hypothesis: Parents randomized to the Immediate group will show improvements in biomarkers of stress system function, in particular the hypothalamus pituitary adrenal (HPA) axis and sympathetic nervous system (SNS) relative to baseline. It is expected that stress-related alterations will be found in parents before the intervention and will improve in those individuals that respond favorably to the treatment. Biomarkers will thus allow an additional level of testing for chronic stress, and efficiency of the intervention; measuring basal HPA axis and SNS activity further allows us to draw conclusions about the adverse long-term health effects of chronic stress and to evaluate the efficiency of the intervention in ameliorating such biological changes.

III. SUBJECT SELECTION

We will recruit through our contacts in the community including other MGH clinicians, as well as through local and national support groups and list serves using IRB approved recruitment materials. MGH child psychologists may also refer potentially eligible participants. Interested participants may call or email the study staff to learn more about the study.

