The current study will employ a pretest-posttest, pilot waitlist controlled design to test the 3RP for parents of children with ASD. Participants will be recruited from local, national, and international organizations, school systems, and hospital clinics.

Inclusion/Exclusion Criteria

Inclusion criteria are:

- 1) Being the parent of at least one child with an autism spectrum disorder
- 2) Age 18 or older
- 3) Can read and speak English

One or more of the following exclusion criteria will render an individual ineligible:

- 1) Unable or unwilling to sign the informed consent documents
- 2) Regular use of corticosteroids at the discretion of the Principal Investigator
- 3) Unable or unwilling to participate in an intervention delivered via videoconferencing.

Recruitment

A total of approximately 70 participants will be recruited for this study. Both males and females from diverse racial and ethnic backgrounds will be recruited using IRB approved procedures. Potential participants will be recruited from our contacts in the community including other MGH clinicians, as well as through local and national support groups and list serves using IRB approved recruitment materials. MGH child psychologists may also refer potentially eligible participants. In each case, interested participants will be directed to our pre-screen REDCap survey and will be given the option to contact the study staff to learn more about the study.

IV. SUBJECT ENROLLMENT

Methods of enrollment

Participants will contact the PI or study staff by telephone, email, or by completing our IRB approved pre-screen REDCap survey in response to advertisements. Subject will be contacted by phone, informed about the study and given an pre-screen REDCap to determine whether they meet inclusion/exclusion criteria (see the attached pre-screening questionnaire). Subjects may also be referred to the study. Subjects must respond "yes" to all inclusion criteria and "no" to all exclusion criteria to be eligible for the study. Eligible participants will be consented and will complete the baseline survey online into REDCap, a secure, web-based application designed to support data capture for research studies.

Randomization

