After enrollment, participants will be randomized to the Immediate intervention group (IG) or Waitlist control group (WG). Randomization will be conducted using a random plan generator, with 1:1 randomization. The WG will begin their program approximately 3 months after the SMART-3RP group. For both groups, the intervention will last approximately 8 weeks, weekly with groups meeting once per week for approximately 1-1.5 hours.

Informed consent process

Eligible and interested participants will be sent a consent form and scheduled for a phone consent. Informed consent and authorization will be obtained and documented through use of a written consent form approved by the Partners Human Research Committee (PHRC) and signed by the participant. The PI or qualified study staff will complete informed consent procedures.

Participants will be asked to read the consent form fully on their own before discussing the consent form with a study staff member (either on the phone or using videoconferencing). The participant will have the opportunity to ask any and all questions about the study. Once all questions have been addressed, they will sign the consent form and send it to the study staff member (either via email, scan, fax, or mail). The study staff member will then sign the participant's signed copy and send a copy back to the participant for their records. As informed consent is a continuous process, participants will be invited to ask questions about their participation at any point over the course of the study.

The consent form will include a description of all study procedures, information about potential risks and benefits of participation, and study contact information (including that of the IRB) in case questions arise at a later time. The consent form will also explicitly state that study participation is voluntary, and that participants may refuse to answer any questions that make them uncomfortable, and may discontinue participation at any time. The consent will also explicitly state that this intervention is psycho-educational and is not clinical care.

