Official Title of Study: Evaluation of a resiliency intervention for parents of children with Autism Spectrum Disorder (ASD)

NCT number: NCT02995408

Date of document: 9/14/16

ASD Study Aims							
Туре	Specific Aim	Hypothesis	Measure	Statistical Test Type			
Primary	To develop and determine the feasibility and acceptibility of an 8-session Relaxation Response Resiliency program for parents of children with ASD	The SMART-3RP virtual delivery will be feasible to implement and acceptable to parents of children with ASD.	
 
assessing the number of sessions attended
 
adherence to Relaxation Response Practice
 
Participant Feedback Survey
 
				
Primary	To test the effectiveness of a pilot waitlist controlled trial on improving resiliency and on improving stress reactivity, growth enhancement, and parental stress	Patients randomized to the Immediate group will report significantly greater scores on the primary outcomes and on the secondary outcomes at 3 mo. post enrollment	
 
General Self-Efficacy Questionnaire (GSE)
 
Current Experiences Scale (CES)
 
Visual Analogue 0-10 scales (stress, distress, coping, and physical discomfort) (VAS)
 
Measure of Current Status-A (MOCS)
 
Cognitive and Affective Mindfulness Scale-Revised (CAMS-R)
 
Parental Stress Scale (PSS)
 
Baseline-3 mo. scores on primary and secondary outcome measures between the Immediate and waitlist control group
 
	
 
paired samples t-tests to compare within group differences from 3 mo. to baseline
 
independent samples t-tests to compare the difference between the Immediate group's 3 months post enrollment and baseline assessment results
 
			

	ASD Study Aims							
Туре	Specific Aim	Hypothesis	Measure	Statistical Test Type				
Secondary	to investigate the extent of pre-post changes in primary and secondary outcomes among participants randomized to both conditions	Scores on primary and secondary outcome measures will improve from pre-post intervention.	• Immediate: assessments from baseline-3 mo.; Waitlist: from 3-6 mo.)	• paired samples t-tests to compare all primary and secondary assessments from pre-post SMART 3-RP				

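### The between-arm questionnaire comparison is an unadjusted t-test on change; adjusting for baseline (ANCOVA) uses the same data, may be much more precise, and costs on average at most about 1.5% in variance at N = 70

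*Protocol*

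**What the plan says.** Protocol Section VI, question 2a, asks whether the arms differ at 3 months. It first plans paired t-tests within each arm. The only between-arm step follows: "We will then use independent samples t-tests to compare the difference between the Immediate" group's change from baseline to 3 months with the Waitlist group's change. It applies to every primary and secondary questionnaire outcome: GSE, CES, four VAS scales, MOCS-A, CAMS-R and PSS, nine scores in all.

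The second Primary row of the SAP table lists "independent samples t-tests to compare the difference between the Immediate" group's 3-month and baseline results. The sentence stops before naming the comparator, but the Measure column of the same row supplies it: "scores on primary and secondary outcome measures between the Immediate and waitlist control group".

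No baseline covariate is named for any questionnaire score. The only model in the plan is for hair cortisol (Section II, Secondary Aim 3: "A mixed effects models approach will be used to examine group" differences in concentration), which is outside this point.

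On size, Section III states: "A total of approximately 70 participants will be recruited for this study". Allocation is 1:1. No power, alpha, effect size, SD, correlation or dropout rate is given.

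**The concern.** A t-test on change already uses the baseline, but it subtracts the whole baseline score whether or not the 3-month score follows it one for one. If the true slope is well below 1, too much is subtracted and baseline noise is carried into the comparison. ANCOVA estimates the slope from the data. Under randomisation both methods estimate the same treatment difference, so the choice is about precision.

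This is the only randomised comparison of the nine scores, and the protocol treats it as a test of effectiveness under Primary Aim 2. With about 35 per arm, a needlessly wide interval on all nine comparisons is worth avoiding when the alternative needs no new data. Section IV lists the baseline survey as an enrolment step ("Eligible participants will be consented and will complete the baseline survey online into REDCap") and places randomisation after enrolment. That baseline precedes allocation is inferred from this order, and it does not affect which test is more precise.

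**Working it through.** **Inputs from the documents.** About 70 participants, 1:1, so 35 per arm; an unadjusted t-test on change. The plan has no power calculation to reproduce.

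**Assumptions.** Correlation rho between baseline and 3 months of 0.3 to 0.9; SD ratio k = SD at 3 months / SD at baseline of 0.8, 1 or 1.25; the same SDs and slope in both arms; independent participants; two-sided 0.05. Baseline SD is set to 1, so the slope is rho × k.

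**Formulas (variance per participant).**
- Change score: 1 + k² − 2·rho·k
- ANCOVA: k²(1 − rho²) × (N − 3)/(N − 4). The last factor is the average cost of estimating the slope, 67/66 = 1.015 at N = 70.
- Before that factor, the change score's excess over ANCOVA is (1 − rho·k)². It is zero only when the slope is 1.

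**Worked case, k = 1, rho = 0.5.** Change: 1 + 1 − 1 = 1. ANCOVA: 0.75 × 67/66 = 0.761. Gain: 1/0.761 − 1 = 31%. The 95% half-width is t × √(2 × variance/35): 0.48 for change (68 df) and 0.42 for ANCOVA (67 df), in baseline SDs.

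**ANCOVA's gain as equivalent extra participants, with 95% CI half-widths (change vs ANCOVA, in baseline SDs):**

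| rho | k = 0.8 | k = 1 | k = 1.25 |
|---|---|---|---|
| 0.3 | 96% (0.51 vs 0.37) | 52% (0.56 vs 0.46) | 26% (0.64 vs 0.57) |
| 0.5 | 72% (0.44 vs 0.33) | 31% (0.48 vs 0.42) | 10% (0.55 vs 0.52) |
| 0.7 | 57% (0.34 vs 0.27) | 16% (0.37 vs 0.34) | 0% (0.43 vs 0.43) |
| 0.9 | 62% (0.21 vs 0.17) | 4% (0.21 vs 0.21) | 4% (0.27 vs 0.26) |

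Simulation with 40,000 trials per cell gave variance ratios within 0.003 of the formula.

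**Where ANCOVA does not gain.** Its worst average variance ratio is 1 + 1/(N − 4), reached at slope 1: 1.5% at N = 70, 1.9% at 56 and 2.6% at 42. With equal SDs, break-even is rho = 2 × 66/67 − 1 = 0.97. At k = 1.25, ANCOVA is slightly worse for rho of about 0.71 to 0.86.

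**Against ignoring baseline altogether.** The change score is less precise than comparing raw 3-month scores when 1 − 2·rho·k > 0, that is, rho below 1/(2k): 0.625, 0.5 and 0.40 for k = 0.8, 1 and 1.25.

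**Power illustration.** For a true difference of half the 3-month SD at rho = 0.5, change vs ANCOVA: 44% vs 66% (k = 0.8), 54% vs 66% (k = 1), 61% vs 66% (k = 1.25).

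**Group delivery.** At 3 months only the Immediate arm has been treated, in groups ("Groups consist of no more than 8 participants, and can be smaller as well"). A group effect adds the same variance to both estimators and so shrinks the relative gain. Assume five groups of 7 with between-group variance 0.05 (k = 1), which adds 0.05/5 = 0.01 to each variance. At rho = 0.5 the gain is (2/35 + 0.01)/(2 × 0.7614/35 + 0.01) − 1 = 0.0671/0.0535 − 1 = 25%. Across rho 0.3 to 0.9 the gains become 43%, 25%, 12% and 2%; at variance 0.10 they are 37%, 22%, 10% and 1%.

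**The case against.** The planned test is prespecified, unbiased and valid, and it matches the paired pre-post tests in the same section. The trial is a pilot with no power target, so none is missed, and the feasibility aim is untouched. All of that stands. It makes this an efficiency point, not an error.

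The benefit cannot be sized from the documents. That also stands: the gain may be nil, and the largest figures need the SD to fall by 20% from baseline, which nothing in the documents supports. But the choice does not require knowing rho, because the possible loss is small and the possible gain is not.

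The 1.5% needs its conditions: it is an average over randomisations with all 70 analysed. In a single data set with slope 1 and a chance baseline imbalance of 0.5 SD, the cost would be 0.5²/(2/35)/68 = 6.4%.

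ANCOVA as proposed also ignores clustering. Simulated with five groups of 7, equal SDs and rho = 0.5, the nominal 5% test has a false-positive rate of about 6.6% (change) vs 7.0% (ANCOVA) at between-group variance 0.05, and 8.5% vs 9.5% at 0.10. Both tests share this fault and ANCOVA has slightly more of it. It is a separate matter and no reason to keep the change score.

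Finally, changing a prespecified comparison late costs credibility, and whether outcomes have already been seen by arm is unknown. This limits how the change can be made.

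**Conclusion.** The point holds. For all nine questionnaire scores, the plan gives up precision that its own data could supply unless the slope of the 3-month score on baseline is close to 1. With 35 per arm, equal SDs and independent participants, the loss is equivalent to 4% to 52% more participants over rho 0.9 to 0.3. Over the wider SD range it runs from nil to 96%, and group effects shrink it. The rho and SD values are assumptions. The direction of the trade rests only on randomisation and N, given a common slope and SDs in the two arms. Nothing here suggests bias or an invalid test, so the change is recommended but not essential to the trial's validity.

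**What to change.** In Protocol Section VI, question 2a, and the second Primary row of the SAP table, replace the independent t-test on change with an ANCOVA for each questionnaire score: the 3-month score regressed on randomised arm, with that participant's baseline score on the same scale as covariate. Report the adjusted Immediate minus Waitlist difference with its 95% CI as the answer to question 2a. The within-arm paired tests and the hair cortisol model need not change.

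The statistical cost is one degree of freedom (68 to 67 with 70 participants) and, on average, at most the 1/(N − 4) in variance shown above. No new data or participants are needed.

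The procedural cost is a dated, justified amendment to both documents, made before outcomes are seen by arm. The SAP is dated 9/14/16 and the protocol 1/14/21, and the Remuneration text in Section V shows that some baseline hair samples were already in. If outcomes have been seen by arm, keep the planned test as the prespecified analysis and report the ANCOVA beside it, labelled as added later.
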